2.0 Objectives

This is a prospective pilot study investigating exhaled breath condensate analyses to quantify the variability over time of various biomarkers associated with SP. Compounds of interest have been chosen due to previous studies demonstrating association with pneumonitis in analyses of serum. Our primary hypothesis is that biomarker concentrations will change over the course of treatment (pre-treatment,

A PILOT STUDY OF EXHALED BREATH ANALYSIS TO ASSESS PNEUMONITIS
DEVELOPMENT AFTER CHEMORADIOTHERAPY FOR STAGE III NSCLC
Wake Forest Baptist Comprehensive Cancer Center (WFBCCC)
WFBCCC 98119

2-weeks on treatment, 6-weeks on treatment, and at 1-month post-treatment, Section 2.1.1). Our secondary hypotheses are that these changes in biomarker concentrations will correlate with SP (Section 2.2.1), which we expect to occur in 15-20% of our patient sample, and that these changes will also occur in serum, which will also correlate with SP (Section 2.2.2). Finally, we hypothesize that pre-treatment EBC-derived microbial signatures will be different in patients who develop SP versus those who do not (Section 2.2.3).

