2.2 Secondary Objectives

- 2.2.1 To examine the associations between differences in pre-treatment and post-treatment *EBC* concentrations of TGF- β 1, IL-6, IL-1 α , and IL-10 and the development of CTCAE grade 2+ SP.
- 2.2.2 To examine the associations between *serum* measures of TGF- β 1, IL-6, IL-1 α , and IL-10 and:
 - 2.2.2.1 *EBC* measures of the same biomarkers, and
 - 2.2.2.2 The development of CTCAE grade 2+ SP.
- 2.2.3 To examine the association between microbiome signatures found in pre-treatment EBC and the development of CTCAE grade 2+ SP.

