4.3.2 Breath Microbiome Analysis

DNA will be extracted from each EBC sample using the QIAamp® UCP Pathogen Mini Kit (Qiagen) with extended homogenization of the breath samples using the Mini-Beadbeater-96 cell disrupter (Biospec Products). The quantity and quality of the DNA extracts will be determined using a DeNovix DS-11 FX+ Spectrophotometer/Fluorometer and Agilent 4200 TapeStation, respectively. The DNA will then be prepared for shotgun metagenomic sequencing using the Nextera® DNA Flex Library Preparation Kit (Illumina). DNA libraries will be normalized and quantified prior to pooling to ensure equal library representation. Pooled DNA libraries will then be sequenced using the Illumina NovaSeq 6000 S1 Reagent Kit and sequencer, generating 2 x 150 bp paired-end reads. Raw sequence reads (FASTQ files) will be imported into the Microbial Genomics Pro Suite within the CLC Genomics Workbench (version 11.0.1; <https://www.qiagenbioinformatics.com>) for QC, adapter trimming, and analysis. High-quality ($\geq Q30$) reads for each sample will be aligned to those in a blank extraction sample (negative control) that will be processed from DNA extraction through library preparation to identify and remove contaminating sequences. The filtered reads will then be aligned to a reference database consisting of complete genomes in the RefSeq database for prokaryotes (bacteria and archaea), eukaryotes (fungi and protozoa) and viruses for taxonomic profiling. The filtered reads will also be assembled into contigs *de novo*, and MetaGeneMark (29) will be used to identify protein-coding regions within the reads to predict functional diversity of the microbiota identified in the samples. The coding regions will be annotated with Pfam domains and GO terms, and the abundance of functional categories will be estimated to build a functional profile for each sample.

The results from the taxonomic and functional profiling will each be merged to estimate similarities and differences among the samples. Heat maps will be generated using Euclidean distance and clustering based on average linkage to assess functional similarities between samples, and principal component analysis (PCA) ordination of Bray-Curtis similarity between samples will be used to visualize the microbiota diversity across the samples.

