5.2 Secondary Outcomes

5.2.1 Concentrations of TGF- β 1, IL-6, IL-1 α , and IL-10 (ng/mL) measured in exhaled breath condensate prior to CRT (baseline), at 2 weeks after CRT start, 6-weeks after CRT start (the end of CRT), and 1

A PILOT STUDY OF EXHALED BREATH ANALYSIS TO ASSESS PNEUMONITIS
DEVELOPMENT AFTER CHEMORADIOTHERAPY FOR STAGE III NSCLC
Wake Forest Baptist Comprehensive Cancer Center (WFBCCC)
WFBCCC 98119

month after completion of CRT compared among patients who develop SP versus those who do not. SP will be assessed at each time point and will be defined as presence of CTCAE version 5.0 grade 2 or higher SP (Appendix C).

- 5.2.2 Concentration of TGF- β 1, IL-6, IL-1 α , and IL-10 (ng/mL) measured in serum prior to CRT (baseline), at 2 weeks after CRT start, 6-weeks after CRT start (the end of CRT), and 1 month after completion of CRT:
 - 5.2.2.1 Compared to concentrations of same biomarkers measured in exhaled breath condensate at same time points (see 5.2.1);
 - 5.2.2.2 and compared among patients who develop SP versus those who do not.
- 5.2.3 Microbial signatures measured in exhaled breath condensate prior to CRT, and presence/absence of SP at study end.

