For our final secondary objective (examining the association between microbiome signatures found in pre-treatment EBC and development of SP) we will use cluster analysis methods to determine whether SP and non-SP patients share similar marker profiles. As stated above, this is a pilot study, therefore these cluster analyses will be considered exploratory and hypothesis generating.

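### The microbiome objective asks whether profiles differ by pneumonitis status, but every planned microbiome analysis is unsupervised, so the plan gives no direct test or effect estimate

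*Combined protocol and SAP*

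**What the plan says.** Three places set the question, and all three frame it by SP status:

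- Section 2.2, objective 2.2.3: "To examine the association between microbiome signatures found in pre-treatment EBC and the development of CTCAE grade 2+ SP".
- Section 2.0, the hypothesis: "we hypothesize that pre-treatment EBC-derived microbial signatures will be different in patients who develop SP versus those who do not".
- Section 5.2, outcome 5.2.3: "Microbial signatures measured in exhaled breath condensate prior to CRT, and presence/absence of SP at study end".

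Section 6.2 gives the analysis in one sentence: "we will use cluster analysis methods to determine whether SP and non-SP patients share similar marker profiles". It adds that "these cluster analyses will be considered exploratory and hypothesis generating". It names no distance, algorithm, number of clusters, rule linking clusters to SP, test, effect measure or interval.

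The laboratory section, 4.3.2, adds two displays. The first concerns functional profiles: "Heat maps will be generated using Euclidean distance and clustering based on average linkage to assess functional similarities between samples". The second, meant for visualising diversity, is described as a "principal component analysis (PCA) ordination of Bray-Curtis similarity between samples". SP is not mentioned in either.

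For the EBC biomarkers, by contrast, section 6.2 plans two-group t-tests of change by SP status and exploratory logistic models for SP, and it plans a similar approach for the serum markers.

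**The concern.** Cluster analysis groups patients by whatever drives most of the variation in the profiles, and it does so without knowing who developed SP. If smoking, oral flora or sequencing depth dominates, the clusters will reflect that. Laying SP status over the clusters afterwards is an indirect comparison. It yields no measure of how strongly profiles and SP are related, and it loses sensitivity when the SP difference is not the main structure in the data.

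Two things are at stake. First, the study could end without a number for objective 2.2.3, although an effect size is what a hypothesis-generating pilot should pass to the next study. Second, with distance, algorithm and number of clusters all open, the choice could be made after seeing which clusters line up with SP.

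**Working it through.** **1. Question against method.** The objective, the hypothesis and the outcome each need SP as the grouping factor. The three planned microbiome analyses are clustering (6.2), heat maps and ordination (both 4.3.2). None uses SP to form groups or axes, and none has a test or estimate attached. Among the secondary objectives that concern SP, the microbiome one alone lacks a supervised comparison.

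**2. The plan's own figures.** No power or effect size is given for the microbiome. The only power table, in 6.1, is for the primary T1-T0 change. It reproduces: with noncentrality d√50 = 2.12, 2.83, 3.54 and 49 df, a two-sided paired t-test at 0.05 has power 0.548, 0.792, 0.934, against the stated 0.55, 0.79, 0.93. It does not bear on objective 2.2.3.

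**3. Number of SP cases.** Section 2.0 expects 15-20%, that is 0.15 × 50 = 7.5 to 0.20 × 50 = 10. Section 6.2 expects 10-15 patients, that is 20-30%. The two agree only at 10, so the check uses 8, 10 and 15.

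**4. Simulation.** The documents supply n = 50 and the SP counts. Everything else is assumed:

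- 60 log-normal taxa, between-patient log-SD 1.0
- 6 of the 30 commonest taxa multiplied by a fixed fold in SP patients
- with and without an unrelated two-group structure
- 400 data sets per setting

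The direct test was PERMANOVA on Bray-Curtis dissimilarity d. For group g, SS_within = Σ_g (1/n_g) Σ_{i<j in g} d_ij² and SS_total = (1/n) Σ_{i<j} d_ij². The effect size is R² = 1 − SS_within/SS_total. The p-value is (1 + number of permutations with SS_within no larger than observed)/(1 + 199).

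The clustering route used average linkage cut at 2 or 3 clusters, or Ward at 2. Each was cross-tabulated with SP by Fisher's test (2 clusters) or a permutation chi-square test (3 clusters).

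Share of data sets with p ≤ 0.05, as the range over SP counts, both structures and, for clustering, all three algorithms (18 cells per row):

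| Fold shift | ln(fold), in log-SD | PERMANOVA | Clusters × SP |
|---|---|---|---|
| none | 0 | 4-7% | 1-4% |
| 2 | 0.69 | 22-45% | 1-11% |
| 3 | 1.10 | 65-90% | 7-39% |
| 4 | 1.39 | 86-99% | 12-64% |
| 6 | 1.79 | 98-100% | 25-88% |
| 10 | 2.30 | 100% | 47-99% |

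The Monte Carlo standard error is at most √(0.5 × 0.5/400) = 0.025. Clustering stayed below 50% in 17 of 18 cells at 4-fold, but exceeded 50% in 10 of 18 at 6-fold and 16 of 18 at 10-fold.

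**5. Other assumed settings.** With 12 of 60 taxa shifted by 0.8 to 1.3 SD, one set of runs (9 SP patients) gave PERMANOVA 51-91% and average linkage at two clusters 4-11%. A second set (9 or 13 SP patients) gave PERMANOVA 71-100%, average linkage at two clusters 2-17% and Ward at two clusters 13-55%. In that second set Ward reached 89-96% at 2.0 SD. The ordering is stable; the sizes are not.

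**The case against.** The strongest reply is that the plan claims little here. Section 6.1 describes the whole study as an exploratory pilot with almost no earlier findings to guide it, and 6.2 labels the cluster analyses hypothesis generating. No error rate, power or confirmatory conclusion is attached to the microbiome. The wording in 6.2 also implies that SP status will be compared with the clusters, so the comparison is under-specified rather than absent. All of this stands: there is no false confirmatory claim. But the label excuses low power and the lack of error control; it does not supply an estimate of the association that the objective names.

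A reader might go further and infer that the plan would usually miss a real difference. The documents do not support that, because they fix no algorithm, number of clusters, decision rule or effect size. Average linkage appears only for the functional heat maps, with Euclidean distance. Cut at two clusters, it is close to a worst case: in the second set of runs in step 5 it isolated a single patient in over half of data sets at 0.8 to 1.3 SD. With 9 SP patients, a one-patient cluster cannot give a Fisher p-value below 9/50 = 0.18. Other clusterings do better, and for very large shifts some find most differences.

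Two more points stand. A global test does not name the taxa that make up a signature, so the descriptive displays remain useful beside it. And PERMANOVA does not rescue small effects.

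**Conclusion.** The concern holds as a mismatch between objective and method. That the plan provides no direct test or effect estimate for objective 2.2.3 follows from the text alone and needs no simulation.

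The loss of sensitivity is assumption-dependent. At 3- to 4-fold shifts in 6 of 60 taxa, a direct test detected about 65-99% against 7-64% for clusters cross-tabulated with SP. The gap narrows for some clusterings at 6-fold and above. At 2-fold both are weak, with the direct test at 22-45%. The direct test's rejection rate without a difference was 4-7%, so its advantage is not bought with false positives. The supported statement is that the planned method is less sensitive and can miss moderate differences. Confidence is moderate.

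The ordination wording in 4.3.2 is an editorial matter. PCA preserves Euclidean distance, whereas a Bray-Curtis matrix is ordinated by principal coordinates analysis or NMDS. The display serves visualisation only, and no conclusion about SP rests on it.

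**What to change.** In 6.2, keep the cluster analysis as description, labelled exploratory as now, and add one pre-specified comparison: PERMANOVA on Bray-Curtis dissimilarity of the baseline EBC taxonomic profiles, one sample per patient, with SP status at study end as the factor. Report R-squared and a permutation p-value. Add a check of within-group dispersion, because the groups will be unequal (about 8-15 against 35-42 if all 50 contribute) and PERMANOVA can respond to a difference in spread as well as in location. State that the result remains hypothesis generating.

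In 4.3.2, as an editorial change, call the Bray-Curtis ordination principal coordinates analysis (or NMDS).

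The cost is a few lines of SAP wording and one extra analysis of data already planned, with no new patients, samples or visits.

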6.3 Analysis of Exploratory Outcome

For the analysis of metabolic measures, we will examine the association of metabolic signatures with development of SP. We hypothesize that metabolic markers in patients who develop SP will be different than those who do not. Therefore, a first analysis will be to examine a series of paired t-tests to determine which markers significantly change between the two time points for patients.

In addition to this analysis, we wish to determine whether there are any marker signatures that appear in groups of patients. To do this we will use cluster analysis methods to determine whether there are any groups of patients who share similar marker profiles at baseline and post-CRT, or change from pre- to post- for metabolic measures. If we are able to identify clusters of patients with common marker signatures, we will then determine whether there are other disease characteristics that are shared by these patients (i.e., tumor stage, lung function, etc.).

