2.3 Exploratory Objective

- 2.3.1 To examine the association between pre- and post-treatment exhaled breath volatile-based metabolites and the development of SP

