4.3.3 Exhaled Breath Volatile Data Generation and Metabolomic Analysis

Unbiased metabolomics analysis of bio-volatiles and biofluids has the potential to identify 100-1000's of metabolites in any single sample. Our

A PILOT STUDY OF EXHALED BREATH ANALYSIS TO ASSESS PNEUMONITIS
DEVELOPMENT AFTER CHEMORADIOTHERAPY FOR STAGE III NSCLC
Wake Forest Baptist Comprehensive Cancer Center (WFBCCC)
WFBCCC 98119

group has successfully assessed bio-volatiles and biofluids by unbiased metabolomics (30, 31). Although there is no single method that allows for the complete analysis of the metabolite, utilizing multiple modes of sample preparation and analysis will potentially identify a number of classes of compounds relevant to this study. The bio-volatile that will potentially be identified are various hydrocarbons, aldehydes, ketones, and alcohols.

Exhaled breath samples will be analyzed using a Markes thermal desorber, TD100-xr, to inject breath samples onto an Agilent two-dimensional GC system 7890B in tandem with LECO's Pegasus 4D Time-of-Flight instrument system (TD-GCxGC-TOFMS). The collected spectra will be processed using LECO's ChromaTOF version 4.72 software. Initial data processing includes peak deconvolution, 1st and 2nd dimension retention time recordings, signal to noise ratio calculation, unique mass detection, peak area determination, and compound identification based on the spectral pattern similarity match against established mass spectral reference libraries (NIST17, 2017 National Institute of Standard Technology, NIH, USA). Identified spectral matches will be aligned using R-program R2DGC (32) to determine common metabolites in patients prior to and after CRT. MetaboAnalyst 4.0 will be employed to normalize and transform the data for univariate and multivariate statistical analysis (33). Additional statistical analysis may be performed using Graphpad Prism 8 (Graphpad Software, Inc).

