5.3 Exploratory Outcome

- 5.3.1 Metabolomic signatures associated with the development of SP. This will include quantitative assessments of metabolic characteristics measured at prior to CRT (baseline), at 2 weeks after CRT start, 6-weeks after CRT start (the end of CRT), and 1 month after completion of CRT. Quantitative assessments of metabolomic assessments measured prior to CRT. Using these three sets of quantitative assessments (at each of the three time points), "signatures" will be developed (described in statistical analysis section) and compared to see whether there are characteristics that remain similar or change when comparing SP and no-SP measures.

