6.2 Analysis of Secondary Outcomes

To examine the association between differences in pre-treatment and post-treatment EBC concentrations of biomarkers and development of SP, we will conduct 2-group independent t-tests comparing mean change levels (from T0 to T1) in each marker among those who developed SP (expected to be around 10-15 patients) to those who remained free of SP at the study end. We will also conduct various exploratory logistic regression models, if numbers permit, to predict the outcome of SP, using various biomarker values (e.g., T0, difference between T0 and T1, etc.) as key predictors. If numbers permit, we will also examine results from repeated measures logistic regression models, using the three repeated measures of the biomarkers as predictors, and/or using at least one delta score as a predictor. Our goal in such exploratory modeling will be to discern what time points or what differences in EBC biomarkers appear to be most highly predictive of occurrence of SP. We will conduct most of this modeling on a single biomarker at a time; based on biological rationale, bivariate findings, and numbers, we may also explore some modeling where more than one biomarker is included.

We also wish to determine to what degree serum levels of biomarkers correlate with levels of the same biomarkers measured in exhaled breath condensate, and how well these serum markers predict SP. For this latter goal, we will use a similar plan as described in the preceding paragraph.

For the former objective (examining how well serum and breath levels of biomarkers correspond), because we do not hypothesize a priori that these 2 different sources of a biomarker are actually measuring (estimating) the same quantity for any of the markers, we do not expect absolute agreement. We will

A PILOT STUDY OF EXHALED BREATH ANALYSIS TO ASSESS PNEUMONITIS
DEVELOPMENT AFTER CHEMORADIOTHERAPY FOR STAGE III NSCLC
Wake Forest Baptist Comprehensive Cancer Center (WFBCCC)
WFBCCC 98119

thus first examine scatterplots of the serum vs breath measure of each biomarker, and if the association appears monotonic in the scatterplot, we will compute Spearman rank correlations. (If the association appears linear and monotonic, we will compute Pearson correlations.) If an association between a serum and breath measure of a biomarker is non-monotonic, we will attempt to fit a curve describing the association most accurately.

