7.3 Study Calendar

	Prior to CRT Start	2-week after CRT Start^e	6-week after CRT Start^e	1 Month after CRT End^e	4 Months after CRT End^e
Informed consent	X				
Demographics	X				
Medical history (Appendix E)	X				
Physical Exam	X				
Pulmonary Function Tests (Appendix H)	X ⁱ				
Antibiotic and Steroid Use (Appendix D)	X	X ^e	X ^e	X ^g	X ^g
Smoking Status (Appendix G)	X	X ^e	X ^e	X ^g	X ^g
Breath Collection (EBC ^a /EBV ^{b,h})	X ^d	X ^e	X ^e	X ^g	
Blood collection ^c	X ^d	X ^e	X ^e	X ^g	
CT chest with or without contrast	X				X ^g
Pneumonitis Evaluation (Appendix C)	X			X ^g	X ^g
Dietary Evaluation (Appendix M)	X ^d	X ^e	X ^e	X ^g	
Radiotherapy Detail Form (Appendix I)	X ^f				

^a Approximately 1-1.5 mL of EBC will be generated in 10 min of breathing

^b 500 ml of EBV in each of 4 collection tubes will be collected in 5-7 min of breathing

^c Blood sample in each redtop (x1) and purpletop (x1) vacutainer blood collection tube

^d Pre-CRT sample collections to occur within 14 days of the date of RT start. It is recommended but not required that this occurs on the date of CT simulation.

^e May occur within +/- 7 days of the scheduled time point measured from the date of RT start. The 2-week after CRT start, 6-week after CRT start, and 1-month after CRT time points will be coordinated with routine blood draws through medical oncology by the study research nurse.

^f To be completed after completion of treatment planning. This may also be completed at any time after CRT has started.

^g May occur within +/- 14 days of the scheduled time point measured from the date of RT end.

^h EBV collection is optional, as defined in Section 4.2.2.

ⁱ Pulmonary function tests must have occurred within 1 year of CRT Start. Results of testing performed at Wake Forest sites or other outside facilities is acceptable.

A PILOT STUDY OF EXHALED BREATH ANALYSIS TO ASSESS PNEUMONITIS
DEVELOPMENT AFTER CHEMORADIOTHERAPY FOR STAGE III NSCLC
Wake Forest Baptist Comprehensive Cancer Center (WFBCCC)
WFBCCC 98119

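### Section 6.3 hypothesises a metabolite difference between patients with and without symptomatic pneumonitis (SP), but names no test of it and no error-rate control

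*Combined protocol and SAP*

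**What the plan says.** The exploratory objective (Section 2.3) is "To examine the association between pre- and post-treatment exhaled breath volatile-based metabolites and the development of SP". On metabolomic signatures, outcome 5.3.1 gives their origin and purpose as follows: "described in statistical analysis section) and compared to see whether there are characteristics that remain similar or change when comparing SP and no-SP measures".

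Section 6.3 opens with the SP association as its aim and gives a between-group hypothesis: "We hypothesize that metabolic markers in patients who develop SP will be different than those who do not". It then names two methods.

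- **Paired tests.** As a consequence of that hypothesis, "a first analysis will be to examine a series of paired t-tests to determine which markers significantly change between the two time points". This is for patients as a whole, with no division by SP.
- **Cluster analysis.** Patients are grouped by marker profile. If clusters appear, the next step is to determine "whether there are other disease characteristics that are shared by these patients (i.e., tumor stage, lung function, etc".

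Section 4.3.3 says the metabolomics platform "has the potential to identify 100-1000's of metabolites in any single sample". On analysis it refers only in general terms to univariate and multivariate methods in a named software package.

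For the breath-condensate cytokines, Section 6.2 does specify the SP contrast: "2-group independent t-tests comparing mean change levels (from T0 to T1) in each marker among those who developed SP", set against those who stay free of SP. The microbiome paragraph of the same section names SP and non-SP patients in its clustering. No multiplicity method appears anywhere in the documents.

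**The concern.** The hypothesis compares two groups of patients. The test drawn from it asks whether the mean change over time differs from zero in all patients pooled. A metabolite can change strongly over chemoradiotherapy (CRT) in everyone and have nothing to do with SP. Another can change only in the SP minority and barely move the pooled mean.

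Followed as written, the first metabolite list would reflect change common to the cohort, yet it would sit under an SP objective and could be read as SP-related. The SP comparison itself would have to be designed after the data are in hand, over a large number of candidate markers and without a stated threshold.

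**Working it through.** **Text check.** For each family of markers, does the plan name a method that uses SP status?

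| Markers | Section | Method using SP status |
|---|---|---|
| Breath-condensate cytokines | 6.2 | Two-group t-test of T0-to-T1 change; logistic models |
| Serum cytokines | 6.2 | Similar plan to the above |
| Microbiome | 6.2 | Clustering with SP and non-SP patients named |
| Breath-volatile metabolites | 6.3 | None named |

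The family with by far the most tests is the one without the contrast.

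**Inputs.** n = 50 and two-sided 0.05 come from Section 6.1, where they are stated for the primary outcome only; using them here is an assumption. SP counts: Section 2.0 expects 15-20%, and 0.15 × 50 = 7.5, 0.20 × 50 = 10; Section 6.2 expects 10-15 patients. I use 8, 10 and 15. Change scores are assumed normal with unit SD.

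**Plan's own figure.** The only power table (Section 6.1) is for a paired comparison of the cytokines. With noncentrality d√50 on 49 df, d = 0.3, 0.4 and 0.5 give 0.548, 0.792 and 0.934, against the stated 0.55, 0.79 and 0.93. It reproduces.

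**Change unrelated to SP.** If every patient shifts by 0.5 SD, the paired test has noncentrality 0.5 × √50 = 3.54 and flags it 93% of the time. An SP versus no-SP test flags it 5% of the time, its null rate.

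**Change in SP patients only.** Let k SP patients shift by 1 SD and the rest by 0.

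- Paired test: the pooled mean shift is k/50. The SD of the pooled scores is about √(1 + k(50−k)/(50 × 49)).
- Two-group test: noncentrality is √(k(50−k)/50) on 48 df.

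| k | Pooled mean shift (SD) | Paired power (simulated) | Two-group noncentrality | Two-group power |
|---|---|---|---|---|
| 8 | 0.16 | 0.17 | 2.59 | 0.72 |
| 10 | 0.20 | 0.23 | 2.83 | 0.79 |
| 15 | 0.30 | 0.47 | 3.24 | 0.89 |

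**Multiplicity.** With m null metabolites tested at 0.05, the expected number of false positives is 0.05m: 5 for m = 100 and 50 for m = 1000. Assuming independence, the chance of at least one is 1 − 0.95^100 = 0.994 for m = 100.

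**With error control.** Apply Benjamini-Hochberg at 10%, assuming 100 to 1000 independent metabolites, 5% of which shift 1 SD in SP patients only. Simulated average power, with ranges running over m:

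| SP cases of 50 | Two-group | Paired |
|---|---|---|
| 8 | 22-29% | under 1% |
| 10 | 34-39% | under 2% |
| 15 | 55-57% | 2-8% |

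**Smaller n.** Note h of the Study Calendar (Section 7.3) says "EBV collection is optional, as defined in Section 4.2.2", so fewer than 50 may contribute. At an assumed n = 30 with 5 to 9 SP cases, unadjusted power is about 12-29% (paired) and 50-68% (two-group). Two-group power under 10% FDR is 4-23%.

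**The case against.** The strongest reply is that this is under-specification in the sole exploratory objective of a 50-patient pilot. Section 6.3 does state the SP association as its aim. It calls the paired tests only a first analysis, and its list of characteristics for the clusters is open-ended, so SP could be meant. In 5.3.1 the pointer to the statistical section attaches most directly to how signatures are developed, which clustering supplies, rather than to the SP comparison later in the same sentence. All of that is fair. It shows that the comparison is intended; it does not supply a method, and no other section does. The exploratory status lowers the weight but does not make the named test answer the stated hypothesis.

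A second reply is that the low paired-test power depends on no-SP patients not changing at all. This is correct as far as it goes. If no-SP patients also shift by 0.2 SD in the same direction, and SP patients keep their 1 SD excess, the paired test flags about 66%, 75% and 90% for 8, 10 and 15 SP cases. If no-SP patients shift by 0.2 SD the other way, it flags about 4%, 4% and 7%. The paired result therefore moves with what the no-SP majority does, while the two-group power does not depend on the common shift. More flags do not help, since none can be attributed to SP.

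Third, the FDR inputs are not in the documents, and the number of metabolites left after alignment may be lower than the platform's potential. Those figures are illustrations only. The textual gap stands without them.

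**Conclusion.** The concern holds. Section 6.3 draws from a between-group hypothesis a test that cannot address it, and no section gives an SP contrast or error-rate control for the metabolites. This should be corrected, but it touches no primary or secondary result.

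On size, the firm statements are that a paired test carries no information on SP status and that 5 false positives are expected per 100 null tests at 0.05. The sensitivity loss (17-47% against 72-89% for a 1 SD change) applies to change confined to SP patients, with n = 50, unit-SD normal change scores and unadjusted two-sided 0.05. Both tests lose power if uptake of the optional breath-volatile collection is partial.

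**What to change.** In Section 6.3:

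1. Make the first analysis a per-metabolite SP versus no-SP comparison of within-patient T0-to-T1 change, matching the two-group test in 6.2, and compare baseline levels as well. Report effect sizes with confidence intervals.
2. State how multiplicity is handled, for example Benjamini-Hochberg at a 10% false discovery rate, and label the results hypothesis generating.
3. Keep the paired t-tests as a description of change over time.
4. If clusters are found, name SP status as a characteristic on which they are compared.
5. Define the time points. Section 6.3 refers to two without naming them, while 5.3.1 lists four and then speaks of three. T0-to-T1 is the main contrast in 6.1; say what role the other samples have.

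The cost is SAP wording and modest analysis time in standard software, with no new samples or patients. Fewer metabolites will be called significant. Under the assumptions above, power at 10% FDR for a 1 SD SP-only change is only about 22-39% with 8-10 SP cases and 55-57% with 15, so the write-up should not present a short list, or an empty one, as evidence of no association.
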